7.3.3 Covariates

In the present study, we have used directed acyclic graphs (DAGs), also called causal diagrams, for confounder selection. DAGs are a well-accepted methodology for using causal knowledge and a set of formal mathematical principles for selecting which variables to adjust for when performing association analyses [Greenland, S., et al 1999]. They provide a systematic way to explore the relationships between the exposures, outcomes, and covariates (unidirectional, bidirectional, causal) and facilitate dealing with a large number of potential confounders. DAGs help make the assumptions underlying an analysis explicit. The selection of variables needed for confounder adjustment to obtain an unbiased estimate of the association under study is called the minimum sufficient adjustment set of confounders. We used the open source and freely available software DAGitty for the development of the DAGs [Textor, J., et al 2011]. DAGitty helps the researcher visualize the structure of relevant variables for the association under study included in the DAG, as well as to identify the minimum sufficient adjustment sets available for confounder adjustment. In the following paragraphs, we present a brief description of the DAG process; however, the full DAG process is described in Annex 8.

The factors listed in the left-hand column of [Table 3](#) were considered potential confounders (i.e., candidate variables) for the association between DL use and seizures, SVT, and/or A-fib/flu based on the literature, as well as consultation with a group of clinical experts. The potential confounders were reviewed during a DAG meeting held on January 6, 2015. At this meeting, the relationships among the different factors were discussed, and DAGitty was used to help identify the minimum sufficient adjustment set of confounders to include in the association analysis of each outcome. Three DAGs including potential confounders of the association between DL use and seizures, SVT, and A-fib/flu, respectively, were developed by the Danish national investigators, MSD, ApEHR, and two clinical experts. After the DAG meeting, we consulted a dermatologist to confirm the correctness of the developed DAGs, especially regarding the relationships between urticaria and the other potential confounders. The DAGs helped clarify whether the potential confounders listed were confounders, colliders, or intermediate variables and which of the potential confounders constituted a minimum sufficient adjustment set. We selected the final minimum sufficient adjustment set, which will be used to adjust for confounding factors in the association studies based on whether we found that a given combination of confounders would be obtainable from the registers. The final minimum sufficient adjustment set for the association studies (i.e., 2B, 3B, and 4B) are seen in the right-hand columns of [Table 3](#).

Table 3 Information on whether potential confounding factors are included in the DAGs and the minimum sufficient adjustment sets, which will be used for confounder adjustment in the association studies.

Potential confounding factors	Potential confounder included in the DAG			Confounders included in the selected minimum sufficient adjustment set for each association study		
	Seizures	SVT	A-fib/flu	Seizures	SVT	A-fib/flu
Age (age will be derived as a categorical and a continuous variable: Age groups [0–4 years, 5–19 years, 20–64 years, ≥65 years] and years)	Yes	Yes	Yes	Yes	Yes	Yes
Sex (male versus female)	Yes	Yes	Yes	Yes	Yes	Yes
Country of residence (Denmark, Finland, Norway, Sweden)	Yes	Yes	Yes	Yes	Yes	Yes
Calendar year (years ranging from 2001–2015)	Yes	Yes	Yes	Yes	Yes	Yes
Drug overdose (other than desloratadine)	Yes	Yes	Yes	No	No	No
Drug and alcohol abuse	Yes	Yes	Yes	No	No	No
Diabetes (both type 1 and type 2)	Yes	Yes	Yes	No	No	No
Use of hypoglycemic agents (oral anti-diabetics, insulin)	Yes	No	No	No	No	No
Hypertension	No	Yes	Yes	No	No	No
Thyroidism (both hypo- and hyperthyroidism, e.g., Grave's disease, thyrotoxicosis)	No	Yes	Yes	No	No	No
Structural heart disease: Left ventricular hypertrophy, left ventricular systolic dysfunction, chronic heart failure (CHF)	No	Yes	Yes	No	No	No
Seasonality (i.e., winter [December-February], spring [March – May], summer [June-August], and autumn [September-November])	Yes	Yes	Yes	Yes	Yes	Yes

Potential confounding factors	Potential confounder included in the DAG			Confounders included in the selected minimum sufficient adjustment set for each association study		
	Seizures	SVT	A-fib/flu	Seizures	SVT	A-fib/flu
Asthmatic status	Yes	Yes	Yes	Yes	Yes	Yes
Disease severity of rhinitis	Yes	Yes	Yes	Yes	Yes	Yes
Chronic obstructive pulmonary disease (COPD)	Yes	Yes	Yes	No	No	No
Smoking	Yes	Yes	Yes	No	No	No
Inflammatory disease	No	Yes	Yes	No	No	No
Metastatic disease	Yes	No	No	No	No	No
Infections	No	Yes	Yes	No	No	No
Stroke	Yes	Yes	Yes	No	No	No
Chronic urticaria	Yes	Yes	Yes	Yes	Yes	Yes
Unspecific autoimmune disease	Yes	Yes	Yes	No	No	No
Type 1 allergy	Yes	Yes	Yes	No	No	No
Antihypertensive treatment	No	Yes	Yes	No	No	No

Table 4 below shows the variables included in the minimum sufficient adjustment sets in all four association analyses. In addition to being confounders included in the association analyses, the variables in the minimum sufficient adjustment sets will be used to characterize the population using DL in the descriptive study of DL use (Substudy 1). The table describes how each of the variables will be operationalized. ICD-10 codes and ATC codes that will be used for the definition of the variables can be found in Annex 6.

Table 4 Definition of confounders included in the minimum sufficient adjustment sets that will be used for confounder adjustment in the association studies.

Confounders included in the minimum sufficient adjustment sets	Definition	Data source
Age	
For the descriptive analyses of DL use, age will be defined as the age of the purchaser at the date of prescription redemption and stratified into age groups (0–4 years, 5–19 years, 20–64 years, ≥65 years).
 
In the association studies, age is a time varying confounder; and therefore, risk time will be split up in years of age. We will evaluate whether age can be included as a continuous variable by examining the assumption of linearity. Alternatively, age will be included as a categorical variable.
	Civil registration system
Sex	Sex is a time-independent confounder and will be included as males versus females in both the descriptive and association analyses.	Civil registration system
Country	Country of residence is a time-independent confounder, as persons will be excluded if emigrating the country. Country of residence will be included with four categories, i.e. Denmark, Finland, Norway, or Sweden in both the descriptive and association analyses.	Civil registration system
Calendar year	
For the descriptive analyses of DL use, calendar year is defined as the year of prescription redemption.
 
In the association studies, calendar year is a time varying confounder; and therefore, risk time will be split up in calendar years.
	Prescription register
Seasonality	
For the descriptive analyses of DL use, seasonality is defined as the season (i.e., winter [December-February], spring [March – May], summer [June-August], and autumn [September-November]) when the DL prescriptions are redeemed.
 
In the association studies, seasonality is a time varying confounder; and therefore, risk time will be split up in seasons defined as winter (December–February), spring (March–May), summer (June–August), and autumn (September–November).
	Prescription register
Asthma status	Both for the descriptive and association analyses, asthmatic status is defined as a binary variable indicating whether or not a person has redeemed treatment for asthma defined as at least two prescriptions of inhalant steroids within a six-month period and/or contacts hospitals with a diagnosis of asthma (including both primary and secondary diagnoses) during a five-year period before first DL exposure. To distinguish persons treated for chronic obstructive pulmonary disease from those treated for asthma, first registered asthma treatment has to be redeemed when the purchaser was 45 years or younger.	National patient register and prescription register

Confounders included in the minimum sufficient adjustment sets	Definition	Data source
Disease severity of rhinitis	Both for the descriptive and association analyses, severity of rhinitis will be defined as binary variable indicating whether or not a person has received treatment for severe rhinitis. Persons with severe rhinitis will be identified from the prescription register as persons who have redeemed immunotherapy at least once during a five-year period before first DL exposure.	Prescription register
Chronic urticaria	Both for the descriptive and association analyses, chronic urticaria status is defined as a binary variable indicating whether or not a person has a registered diagnosis of chronic urticaria in the five-year period before first DL exposure.	National patient register

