7.4 Data Sources

The DL study will include register information from four Nordic countries – Denmark, Finland, Norway, and Sweden. In addition to a long history of collecting high quality information on births, deaths, immigration and emigration, disease incidence, and activities in the healthcare sector [Thygesen, L., et al 2011], exceptional opportunities to perform register-based research are driven by the unique PIC introduced in the Nordic countries in the 1960's and available to all persons with permanent residence in the Nordic countries [Pedersen, C. B. 2011]. The PIC makes it possible to link information at the individual level from several registers for scientific research purposes. The national prescription registers and national patient registers within each of the Nordic countries capture all the individual encounters of purchasing prescribed DL and allow sufficient longitudinal data to differentiate between first and recurrent seizures, as only first seizure will be analyzed, and to identify incident SVT and A-fib/flu cases. Person-specific use of DL will be elucidated from the

national prescription registers by obtaining information on redemption of DL prescription for each person [Furu, K., et al 2009]. Person-specific information on seizures, SVT, and A-fib/flu will be derived from the Nordic national patient registers.

Table 5 presents key information on the population-based health registers in the Nordic countries of relevance for the present study. Data will be available until and including 2015 for all countries. The data extraction period refers to the longest period for which data on exclusion variables (e.g., seizures, SVT, or A-fib/flu before baseline) can be obtained for.

Table 5 Overview of national health registers in the Nordic countries of relevance for the present study.

Register	Country			
	Denmark	Finland	Norway	Sweden
National prescription register	1995–2015	1994–2015	2004–2015	2005–2015
National patient register	1977–2015 (1)	1967–2015 (2)	2008–2015	1987–2015 (3)
Civil registration system	1968–2015	1967–2015	1964–2015	1965–2015
Study period	2001–2015 (15 years)	2001–2015 (15 years)	2008–2015 (8 years)	July 2005–2015 (11 years)
Data extraction period	1977–2015	1967–2015	2008–2015	1987–2015

(1) Contacts with outpatient clinics (incl. emergency departments) since 1995.

(2) Contacts with outpatient clinics (incl. emergency departments) since 1998.

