7.7.1 Substudy 1: Descriptive analysis of exposure of DL

A cohort study describing DL use in the general population will be performed. A person with prescription redemption of DL in Norway and Sweden within the first 6 months after establishment of the prescriptions registers will not be included in order to avoid left-truncation bias. In addition, to avoid analogous misclassification of prevalent with incident DL dispensings among immigrants, we exclude persons with DL prescription redemptions within 6 months after immigrating to Denmark, Finland, Norway, or Sweden. Prevalent users will be defined as persons who have at least one prescription of DL in the period of interest (e.g., the entire study period or each year). Incident users are first time users of DL in the period of interest. The following descriptive analyses will be performed:

- The distribution of prevalent and incident users in the total population and stratified by country, age, sex, calendar year, seasonality, severity of rhinitis, asthmatic status, and chronic urticaria status.
- Descriptive information on the mean, standard deviation, median, and maximum and minimum number of redeemed DL prescriptions in the total population and stratified by country, age, sex, calendar year, seasonality, severity of rhinitis, asthmatic status, and chronic urticaria status.

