- Left-truncation is a potential bias in the study meaning that we have no information on DL use before the start of registration of prescriptions in each country. Left-truncation bias in relation to DL use is only a relevant issue for Sweden and Norway since DL was available from 2001, but the prescription registers in Norway and Sweden were established in 2004 and 2005, respectively (Table 4). Therefore, we do not know whether a DL user in the first year of registration in Norway and Sweden is a long-term user (prevalent user) or a first-time user (incident user). To account for this potential bias, a person with prescription redemption of DL in Norway and Sweden within the first 6 months after establishment of the prescriptions registers will not be included. This is not a limitation in Denmark and Finland since DL was first approved in 2001 and the prescription registers in Denmark and Finland were established in 1995 and 1994, respectively. However, left-truncation bias might also occur when persons are immigrating into the study population. Therefore we also exclude persons with DL prescription redemptions within 6 months after immigrating to Denmark, Finland, Norway, or Sweden.
- There is a possibility that patients could purchase DL over-the-counter; however, because of reimbursement systems in the Nordic countries, it is actually less expensive to purchase prescription DL. In Norway and Sweden DL has only been allowed for prescription sale; However, in Denmark, DL has been available for over-the-counter sale since 2013, but over-the-counter sales only counted for less than 4 % of the total amount of DL purchased in 2013. A supplementary analysis will examine the associations under consideration restricting the time period to include only years where DL was not allowed for OTC sale.
- Loratadine, the parent compound of DL, is also available via prescription and over-the counter in the Nordic countries. We think it is somewhat unlikely that patients would switch between DL and loratadine. However, it is possible that some of the time counted as unexposed in the analyses could actually be time exposed to loratadine or over-the-counter DL. Moreover, other non-sedating prescription antihistamines are available in the Nordic countries, and if the effect on the outcomes

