- The present study aims at studying incident outcomes occurring in the community setting. To differentiate between incident and prevalent disease, we exclude persons with registered disease before baseline. In addition, we used surrogates of prevalence (i.e., redeemed prescriptions of antiepileptic medicine) to exclude persons with prevalent disease. To capture disease cases emerging in the community setting, we limit ascertainment to those sites of care where incident presentation would be present and use only primary diagnoses of hospitalization, as secondary diagnoses often represent conditions emerging during hospitalization.

Confounders

In the present study, we expect complete information on the central confounders of age, sex, calendar year, country, and seasonality, as these are measured as key variables in the registers and information on these variables has to be entered into the system to establish a record file.

Information on the three confounders of severity of rhinitis, asthmatic status, and chronic urticaria status is challenging to obtain from the nationwide registers for many reasons. First of all, these conditions in general emerge in the primary health care sector where patients normally seek care from their general practitioner for treatment of symptoms. Second, truncation bias may, as with regard to the measures of exposure and outcome, also occur in relation to these three confounders in Norway as the patient register was established in 2008, making the follow-up period rather short. Third, different issues regarding codes and use of drugs for the three conditions have to be realized and discussed to understand the potential impact of residual confounders in the present study. We have discussed these issues with clinical experts and the essence of the discussion is given below.

- Severity of rhinitis is measured as use of immunotherapy and the binary measure of severity of rhinitis will not capture different levels of disease severity. Therefore, we expect the sensitivity of the measure to be rather low and severity of rhinitis to be underreported in the present study. However, we do not expect misclassification of those persons who received immunotherapy, as it is assumed that persons receiving immunotherapy also have severe rhinitis. A quantitative bias analysis examining the impact of misclassification of severity of rhinitis on the results will be performed.

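### The fixed five-year look-back for rhinitis severity, asthma and chronic urticaria is unavailable for some countries and years, and section 7.9 admits this only for Norway's patient register

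*Protocol*

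**What the plan says.** Section 7.3.3, Table 4, makes three of the eight adjustment variables binary, each decided by what the registers hold before a person's first DL redemption.

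- Rhinitis severity, from the prescription register alone: "persons who have redeemed immunotherapy at least once during a five-year period before first DL exposure".
- Asthma, from both registers: at least two inhaled-steroid redemptions within six months, and/or "contacts hospitals with a diagnosis of asthma (including both primary and secondary diagnoses) during a five-year period before first DL exposure". In addition, "first registered asthma treatment has to be redeemed when the purchaser was 45 years or younger".
- Chronic urticaria, from the patient register alone: "a registered diagnosis of chronic urticaria in the five-year period before first DL exposure".

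Section 7.7.1 describes DL use "stratified by country, age, sex, calendar year, seasonality, severity of rhinitis, asthmatic status, and chronic urticaria status". Sections 7.7.2 to 7.7.4 adjust the Poisson models for the same list.

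On register history, section 7.9 notes under exposure that "the prescription registers in Norway and Sweden were established in 2004 and 2005, respectively". For the three covariates it says only that truncation may "also occur in relation to these three confounders in Norway as the patient register was established in 2008".

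**The concern.** A five-year window gives the same variable everywhere only if every register reaches back five years before first DL. Section 7.3.1 normally reads an absent prescription record as non-use, and Table 4 has no rule for a person whose available history is shorter than five years. Such a person is coded as not having the condition, so the same negative value means different things by country and by year of first DL use.

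This matters most for Substudy 1, a primary objective, which reports DL use by these variables. It also matters for comparisons between countries. The purpose of this protocol is to analyse Norway alone and combined with the other three countries, and supplementary analysis 4 in section 7.7.5 stratifies 2B, 3B and 4B by country.

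The limitations text would also mislead. Sweden, which has the shortest prescription history, is not named for the covariates. Norway is named for a patient-register reason that cannot touch rhinitis severity, because that variable does not use the patient register.

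**Working it through.** The protocol gives no figure for this point, so the check is date arithmetic on Table 5 and its footnotes.

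**Formula.** First date with full look-back = register start + 5 years. Incomplete share = eligible months before that date / all eligible months to December 2015.

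| Country | Study start | Prescriptions: start, full from | Inpatient: start, full from | Outpatient: start, full from |
|---|---|---|---|---|
| Denmark | 2001 | 1995, 2000 | 1977, 1982 | 1995, 2000 |
| Finland | 2001 | 1994, 1999 | 1967, 1972 | 1998, 2003 |
| Norway | 2008 | 2004, 2009 | 2008, 2013 | 2008, 2013 |
| Sweden | July 2005 | 2005, Jan-July 2010 | 1987, 1992 | 2001, 2006 |

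**Sweden, prescriptions.** Table 5 gives the register start only as 2005, so both ends of a range are shown. Persons who redeem DL in the register's first six months are excluded (7.7.1 to 7.7.4).

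- Start July 2005: eligible from January 2006, 120 months in all. January 2006 to June 2010 is incomplete: 54/120 = 45.0%.
- Start January 2005: eligible from July 2005, 126 months in all. July 2005 to December 2009 is incomplete: 54/126 = 42.9%.

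Either way the earliest eligible user has about 6 of 60 months of look-back, and the mean over the 54 months is (6 + 60)/2 = 33 months.

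**Norway.** Hospital diagnoses: 60/96 = 62.5% of months incomplete, with no look-back in January 2008. Prescriptions: 12/96 = 12.5%.

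**Finland.** Outpatient diagnoses: 24/180 = 13.3%.

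**Sweden, hospital diagnoses.** Inpatient is complete throughout. Outpatient is complete from January 2006, so at most 6/126 = 4.8% of months are short.

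**Illustration of lost capture (assumptions, not in the protocol).** Suppose immunotherapy lasts c months at a random time and first DL dates are spread evenly. With w months of look-back, the share of truly positive persons captured is (c + w)/(c + 60).

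- c = 0 (single redemption): 33/60 = 55% on average over the 54 Swedish months, 6/60 = 10% for the earliest user.
- c = 36: 69/96 = 72% on average, 42/96 = 44% for the earliest user.

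**The age-45 condition.** Take a person aged 48 in 2006 who has used inhaled steroids since age 30. In Denmark the first registered redemption falls at about age 37 (register from 1995), or about 43 if only the five-year window counts, so the person qualifies. In Sweden it falls at about 47, so the steroid arm fails. A hospital diagnosis could still classify the person as asthmatic.

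**The case against.** Much can be said for the plan.

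- Norway's hospital gap is already disclosed in 7.9. The 62.5% puts a size on an admitted limitation.
- Section 7.9 plans quantitative bias analyses for misclassification of all three variables and concedes low sensitivity or under-reporting. Section 7.6 requires each country's data control report to state known misclassification.
- The association analyses use DL users only. The same person may contribute exposed and unexposed time, and 7.1 chose this to reduce confounding by time-independent factors. The three covariates are fixed at first DL, and the models also adjust for country and calendar year.
- Supplementary analyses are to be detailed in the SAP, which is not at hand.

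Most of this stands, and it limits the point. Some of it does not fully answer the point. The bias analyses are motivated by coarse coding, overlap with chronic obstructive pulmonary disease and diagnostic delay, not by look-back that varies with country and period. Calendar year in the models is split risk time, whereas look-back length depends on the year of first DL. Adjustment cannot reclassify individuals, and it does nothing for the descriptive shares in Substudy 1. None of the analyses listed in 7.7.5 addresses look-back. The definitions and the limitations text are set in the protocol itself.

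A reader might infer that all three variables are short in Sweden until 2010. Table 5 does not support that for urticaria, nor for the hospital arm of asthma. A reader might also infer that confounding control fails in 2B, 3B and 4B. No bias in a rate ratio has been shown. Nor does 7.7.1 say that the strata are crossed by country and year, so a visible artificial time trend depends on how the tables are laid out. Understated pooled shares do not.

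**Conclusion.** The point holds in limited form. Table 4's look-back cannot be met for Swedish prescription-based items before January to July 2010 (43-45% of eligible months), Norwegian hospital diagnoses before 2013 (62.5%), Norwegian prescriptions in 2008, or Finnish outpatient diagnoses in 2001-2002. These are shares of calendar months of first DL use, not of users.

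Following the plan will understate severe rhinitis and asthma among early Swedish users, and hospital-diagnosed urticaria and asthma among Norwegian users before 2013. Section 7.9 is incomplete on this, and its stated reason does not fit rhinitis severity. The main consequence is for Substudy 1 and for comparisons between countries. The effect on the incidence rate ratios is probably modest and remains unquantified. The dates rest on Table 5, with the Swedish start month unknown. The capture percentages are illustrative only.

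**What to change.** 1. In Substudy 1, present each stratifier also, or only, for first DL dates with complete look-back in the register it uses.
   - Rhinitis severity: Denmark and Finland all years, Norway from 2009, Sweden from January to July 2010 according to the actual register start.
   - Chronic urticaria: Denmark all years, Finland from 2003, Sweden from 2006, Norway from 2013.
   - Asthma: the later of the two register dates in each country.
2. Add to 7.7.5 one sensitivity re-run of 2B, 3B and 4B, restricted to persons whose look-back is fully covered by both registers for five years, or since birth if younger than five at first DL. The since-birth clause is needed because a plain five-year requirement would remove every child under five at first DL and nearly empty the 0-4 stratum. The full cohort stays primary.
3. Correct 7.9 to name Sweden, and Norway in 2008, for the prescription-based variables, and Finland in 2001-2002 for outpatient diagnoses.

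The cost is protocol and SAP wording plus one re-run on data already held. The restricted analysis will have fewer events and wider intervals.
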